## **10. SAFETY ANALYSES**

The safety analysis will be performed based on the Safety Population, unless otherwise specified. Safety parameters will include adverse events (AE), clinical laboratory parameters, vital signs, ECG, [REDACTED].

For each safety parameter other than AE, the last non-missing assessment made before the first dose of study drug will be used as the baseline for all analyses of that safety parameter.

### **10.1 Adverse Events**

Adverse events (AEs) will be coded using the latest version of MedDRA.

An AE (classified by preferred term) is considered a treatment-emergent adverse event (TEAE) if it started as a new event or if an AE severity increased from the time of the first dose of study drug until 10 days after the last dose of study drug. A new event is an event that either did not occur before, or started 2 days or more after, the end date of the previous event for the same preferred term. Severity increase refers to an increase in AE severity for a continuous event.

The number and percentage of subjects reporting TEAEs by cohort and treatment, ITI-333 combined across all cohorts, and placebo combined across all cohorts will be tabulated by SOC and preferred term; by SOC, preferred term, and severity; and by SOC, preferred term, and relationship to study drug. If there is more than one AE that is coded to the same preferred term for the same subject, that subject will be counted only once for that preferred term using the most severe for the summarization by severity and most related occurrence for the summarization by relationship to study drug.

The incidence of serious adverse events (SAEs) and of AEs leading to premature discontinuation of the study drug by cohort and treatment, ITI-333 combined across all cohorts, and placebo combined across all cohorts will also be summarized by SOC and preferred term. Listings will be presented for SAEs, AEs leading to discontinuation of study drug, and subjects who died based on the Enrolled Population.

AEs will be reviewed for any evidence suggestive of abuse potential using standardized MedDRA queries (SMQs) for drug abuse, dependence, and withdrawal. Adverse events identified through SMQs by cohort and treatment, ITI-333 combined across all cohorts, and placebo combined across all cohorts will be summarized by preferred term. A supportive listing will be presented for drug abuse and dependence AEs.

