Duration of Treatment	Study duration includes a Screening Period up to 21 days prior to dosing on Day 1, an inpatient Treatment Period of up to 17 days, and a Safety Follow-up Visit 10 days (\pm 1) day after the last dose of study drug. Therefore, the total study duration for each subject will be up to 46 days, including the Screening Period.
Test Product, Dosage, and Mode of Administration	
ITI-333 [REDACTED] will be supplied to the study center by the Sponsor [REDACTED]. [REDACTED] The planned ITI-333 doses in each cohort are:
 
 • Cohort 1: 0.75 mg ITI-333 once daily for 14 days • Cohort 2: 1.5 mg ITI-333 once daily for 14 days • Cohort 3: 3 mg ITI-333 once daily for 14 days • Cohort 4: 6 mg ITI-333 once daily for 14 days. 
Dose escalations other than the planned dosed specified above may be evaluated based on safety and PK assessments but they will not exceed 2-fold. [REDACTED]

Reference Product, Dosage, and Mode of Administration	Placebo [REDACTED], once daily for 14 days.
Pharmacokinetic Measures	
Blood samples to determine plasma concentrations of ITI-333 [REDACTED] will be collected at the following timepoints:
 
 • [REDACTED] • Day 14: predose, 0.5, 1, 1.5, 2, 3, 4, 6, 8, 12, 24, 48, and 72 hours postdose.
Safety Measures	
The safety and tolerability of ITI-333 will be assessed throughout the study via:
 
 • Adverse events (AEs) • Vital signs (blood pressure, [REDACTED] SpO₂, [REDACTED] weight, and body mass index [BMI]) • 12-lead electrocardiogram (ECG) • Clinical laboratory tests [REDACTED] • Prior and concomitant medications • Physical examination • [REDACTED] • Pregnancy test (where applicable)
[REDACTED]	[REDACTED]

[illegible]

• [REDACTED]
Plasma concentration data of ITI-333 [REDACTED]

[REDACTED] will be listed by subject using the Safety Population. For each analyte, plasma concentrations will be summarized using descriptive statistics by cohort, treatment day, and nominal sampling time using the PK Population. Descriptive statistics will be used to summarize PK parameters of ITI-333 [REDACTED] by cohort, using the PK population.

Safety Analysis:

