6. INVESTIGATIONAL PLAN

6.1 Overall Study Design and Plan

This study will be conducted as a single-center, randomized, double-blind, placebo-controlled, dose escalation study of ITI-333 in up to 4 sequential cohorts with 8 healthy male and female subjects to be randomized in each cohort, for a total of approximately 32 subjects. The study will be performed at 1 study center in the United States.

The study will be conducted as follows:

- A Screening Period of up to 21 days prior to dosing on Day 1
- A Treatment Period from Days 1-17
- A Safety Follow-up (SFU) Visit on Day 24 ± 1.

Following Screening, eligible subjects will be admitted to the study center on Day -1. On Day 1, subjects will be randomized to receive an oral dose of either ITI-333 (n=6) or placebo (n=2) once daily for 14 days. The planned doses in each cohort are as follows:

- Cohort 1: 0.75 mg ITI-333 (n=6) or placebo (n=2)
- Cohort 2: 1.5 mg ITI-333 (n=6) or placebo (n=2)
- Cohort 3: 3 mg ITI-333 (n=6) or placebo (n=2)
- Cohort 4: 6 mg ITI-333 (n=6) or placebo (n=2).

[REDACTED]

Sentinel dosing will be used in each cohort: the first 2 subjects in each cohort will receive either ITI-333 or placebo. Dosing of the remaining subjects within each cohort (5 subjects will receive ITI-333, 1 subject will receive placebo) will occur after a minimum of 24 hours from the Day 7 dosing of the sentinel group, to ensure adequate evaluation of safety and tolerability by the Investigator and Sponsor Study Physician.

A DMC will review safety and PK data to determine the progression of dose escalation before proceeding to the next cohort. Details related to the DMC and the review of the data will be provided in the DMC charter. Dosing for the next higher dose cohort will not begin until the dose in the preceding cohort is deemed safe and tolerable. Dose escalations other than the planned doses specified above may be evaluated based on safety and PK assessments but they will not exceed 2-fold.

[REDACTED]

[figure not shown]
[REDACTED]

[REDACTED]

[figure not shown]

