8.1.1.4 Time Period and Frequency of AE and SAE Reporting

The Investigator will report all AEs/SAEs from the time informed consent was obtained until 30 days after the last dose of study drug.

At each visit, subjects are to be queried regarding any AEs that have occurred since the previous visit. Subjects will be asked to volunteer information with a nonleading question such as, "How do you feel since your last visit?"

All AEs must be followed to satisfactory resolution, until the Investigator deems the event to be chronic or not clinically significant, or until the subject is considered to be clinically stable.

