9.4.5.1 Adverse Events

Adverse events (AEs) will be coded by preferred term and system organ class (SOC) using the latest version of Medical Dictionary for Regulatory Activities (MedDRA).

An AE (classified by preferred term) is considered a treatment-emergent adverse event (TEAE) if it starts as a new event or if an AE severity increases from the time of the first dose of study drug until 10 days after the last dose of study drug. A new event is an event that either did not occur before, or started 2 days or more after, the end date of the previous event for the same preferred term. Severity increase is referring to an increase in severity during the treatment period for a continuous event.

The number and percentage of subjects reporting TEAEs by cohort and treatment, ITI-333 combined across all cohorts, and placebo combined across all cohorts will be tabulated by SOC and preferred term; by SOC, preferred term, and severity; and by SOC, preferred term, and relationship to study drug. If there is more than one AE that is coded to the same preferred term for the same subject, that subject will be counted only once for that preferred term using the most severe and most related occurrence for the summarization by severity and relationship to study drug, respectively.

The incidence of serious adverse events (SAEs) and of AEs leading to premature treatment discontinuation of the study by cohort and treatment, ITI-333 combined across all cohorts, and placebo combined across all cohorts will also be summarized by SOC and preferred term. Listings will be presented for SAEs, for AE leading to treatment discontinuation, and for subjects who died.

AEs will be reviewed for any signal suggestive of abuse potential using standardized MedDRA queries for drug abuse, dependence, and withdrawal.

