## **9. EXTENT OF EXPOSURE AND TREATMENT COMPLIANCE**

### **9.1 Extent of Exposure**

Each subject will receive an oral dose of study drug once daily for 14 days. Exposure to study drug will be summarized for treatment duration, calculated as the number of days from the date of the first dose of study drug taken to the date of the last dose taken, inclusive. Descriptive statistics (n, mean, median, SD, minimum, and maximum) for exposure to study drug will be presented by cohort and treatment, ITI-333 combined across all cohorts, and placebo combined across all cohorts for the Safety Population.

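### The TEAE window ends one day before the last permitted follow-up visit day, and the Protocol and SAP treat late severity increases differently

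*SAP*

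**What the plan says.** SAP 10.1 makes an AE treatment-emergent "if it started as a new event or if an AE severity increased from the time of the first dose" up to a closing point 10 days after the last dose. The full window reads "from the time of the first dose of study drug until 10 days after the last dose of study drug". Protocol 9.4.5.1 has the same 10-day limit.

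Three other time limits bear on it:

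- **Follow-up visit.** Protocol 6.1 schedules "A Safety Follow-up (SFU) Visit on Day 24 ± 1". Protocol 6.4 gives the same timing relative to dosing, 10 days with a tolerance of 1 day.
- **AE collection.** Protocol 8.1.1.4 has AEs and SAEs reported "from the time informed consent was obtained until 30 days after the last dose of study drug".
- **Severity increase.** Protocol 9.4.5.1 goes on to define this as "an increase in severity during the treatment period for a continuous event". SAP 10.1 keeps the idea of a continuous event but drops the restriction to the treatment period. SAP 17 nevertheless states that the protocol analyses are unchanged.

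**The concern.** The safety follow-up visit is the last scheduled opportunity to find an adverse event, and the counting window closes before that visit's own tolerance does. A finding with no earlier symptom, such as a clinically significant laboratory value, would ordinarily be dated to the day it was detected. Two subjects with the same finding at equally compliant visits, one on Day 24 and one on Day 25, would then be classified differently for a reason unrelated to the drug.

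The severity wording raises a separate problem. The Protocol's main TEAE sentence covers worsening up to 10 days after the last dose, but its explanatory sentence limits worsening to the treatment period. The SAP follows the first and omits the second, and does not record the difference.

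Safety and tolerability are stated objectives, the analysis is descriptive, and the cohorts are small. Incidence tables by cohort are a main output, and one reclassified subject is visible in them. The drug is a mu-opioid partial agonist stopped after 14 days, so events arising after the last dose are of interest.

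**Working it through.** **Inputs**

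- Dosing: "Each subject will receive an oral dose of study drug once daily for 14 days" (SAP 9.1), so the last dose is on Day 14 for a subject who completes dosing.
- Screening: up to 21 days (Protocol 6.1).
- Follow-up visit: Day 24 ± 1 (Protocol 6.1).
- Discharge: Day 17 (Protocol synopsis). Treatment period: Days 1-17 (Protocol 6.1).
- TEAE window: last dose + 10 days. AE collection: last dose + 30 days.

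**Reproducing the plan's own figure.** The synopsis says "the total study duration for each subject will be up to 46 days". Screening 21 + last dose day 14 + 10 + tolerance 1 = 46. The figure reproduces exactly and confirms that Day 25 is the latest on-schedule follow-up visit.

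**Limits on the study-day scale**

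| Limit | Arithmetic | Day |
|---|---|---|
| TEAE window closes | 14 + 10 | 24 |
| Earliest follow-up visit | 14 + 9 | 23 |
| Latest follow-up visit | 14 + 11 | 25 |
| AE collection ends | 14 + 30 | 44 |

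The window is 25 − 24 = 1 day shorter than the visit tolerance, so 1 of the 3 permitted visit days lies outside it.

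**What a Day 25 visit loses.** The rule works on onset or worsening, not on detection. Protocol 8.1.1.4 says "At each visit, subjects are to be queried regarding any AEs that have occurred since the previous visit". With discharge on Day 17, a Day 25 visit looks back over Days 17-25, which is 9 calendar days. Onsets on 8 of them (Days 17-24) are still TEAEs. Only onset or worsening dated to Day 25 itself falls outside.

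**Days after the visit.** Days 25-44 are 44 − 24 = 20 of the 30 post-dose collection days (20/30 = 67%). This counts calendar days, not expected events. Protocol 6.1 lists no later visit, and Protocol 8.1.1.5.1 provides for one only if safety surveillance needs it.

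**Severity increases.** The treatment period ends on Day 17 and the TEAE window on Day 24, so the two documents differ over Days 18-24, 24 − 17 = 7 days. An AE that began after the first dose is already a TEAE as a new event. The difference therefore changes TEAE status mainly for an event already present before dosing that worsens in those 7 days. If sites record a worsening as a separate entry, it could also change the severity tables; the visible text does not give the recording convention.

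**Weight of one subject.** 1/6 = 16.7 percentage points in one ITI-333 cohort; 1/24 = 4.2 points in ITI-333 combined over four cohorts (4 × 6 = 24).

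**Effect of changing the limit.** Last dose + 11 days closes on Day 25 and covers every on-schedule visit. Last dose + 30 days closes on Day 44 and leaves no collected post-dose AE outside.

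**The case against.** The 10-day limit is prespecified, is the same in both documents, recurs in SAP 16.2.4, and coincides with the nominal follow-up day. Nothing in the documents requires the TEAE window to equal the reporting period, and the visible text gives no half-life from which to argue that 10 days is too short. That stands. The length of the window is a choice, and no conflict between the documents arises from it.

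A reader might infer several stronger things that the documents do not support:

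- **That any AE found on Day 25 or later drops out.** It does not if it began by Day 24.
- **That late events disappear from the results.** The summaries of SAEs, of AEs leading to discontinuation of study drug, and of AEs found by the standardized queries for abuse, dependence and withdrawal are not worded as TEAE-only. The off-drug opioid question is therefore not confined to the 10-day window as written. SAP 16.1.1 also uses all postbaseline assessments for PCS determinations and lists every assessment, so an abnormal Day 25 measurement remains visible.
- **That later AEs are not presented anywhere.** Table and listing specifications are in a separate document (SAP 2), so a listing of them cannot be ruled out.
- **That the 46-day duration is wrong.** It runs to the follow-up visit and reproduces exactly. Reporting obligations after that visit need not be included.

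None of this answers the one-day mismatch with the visit tolerance or the unrecorded difference in the severity wording.

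**Conclusion.** The point holds as a minor alignment item. Non-serious AEs dated to an on-schedule Day 25 visit are not TEAEs, although the same findings on Day 23 or 24 would be. Worsening on Days 18-24 is a TEAE under the SAP but not clearly one under the Protocol, while SAP 17 reports no changes. Few events are likely to be affected, but each would be one subject in a cohort of 6.

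The conclusion rests on these assumptions:

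- The subject completes 14 doses. After early discontinuation, the same 10-, 11- and 30-day offsets apply from the actual last dose.
- The 10 days are calendar days that include all of Day 24. If they mean 240 hours, onsets later on Day 24 than the dosing time would also fall outside. The text does not say which.
- A finding without earlier symptoms is dated to the visit at which it is detected. Neither document gives an onset-dating rule, and the assessments done at follow-up are not visible.

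A 30-day window is optional; the documents do not establish that it is needed.

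**What to change.** In Protocol 9.4.5.1 and SAP 10.1:

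1. End the TEAE window at the later of 10 days after the last dose and the actual date of the safety follow-up visit. State that the limit is in calendar days. If no follow-up visit takes place, the 10-day limit applies.
2. Use the same window for severity increases, by removing the restriction to the treatment period from the Protocol's explanatory sentence. The SAP 17 statement would then be correct on this point. If the Protocol is not amended, record the difference in SAP 17.
3. List AEs with onset after the window and up to 30 days after the last dose separately by treatment.
4. Bring the 10-day reference in SAP 16.2.4 into line.

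The cost is one rule in the text and the programs. A few unrelated AEs may enter the tables, but they are shown against placebo under the same rule. The window will differ by a day between subjects according to visit date, and will stretch further if a visit is late. A fixed limit of 11 days would avoid that and still cover every on-schedule visit.

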4. INTRODUCTION

ITI-333 uniquely combines high affinity binding to μ -opioid and serotonin 5-HT_{2A} receptors. In addition to the potential benefits conferred by ITI-333 affinity for μ -opioid receptors, the affinity of ITI-333 for 5-HT_{2A}, in concert with μ -opioid receptors, suggests a potentially unique functional pharmacological interaction that may have utility in the treatment of opioid use disorder (OUD) and the associated psychiatric comorbidities (eg, depression and anxiety).

Nonclinical data demonstrate that ITI-333 functions as a biased μ -opioid receptor ligand with partial agonist activity, acting as an antagonist to block effects of high doses of morphine in both pain and motor activity models while acting alone to provide potent analgesia in models of acute and chronic pain. However, when given to rodents at doses comparable to those that block the effect of morphine and well in excess of those required for analgesia, ITI-333 elicits no signs of physical dependence or tolerance after chronic dosing or after abrupt withdrawal of the compound.

In models designed to evaluate the safety pharmacology, ITI-333 did not induce biologically relevant effects on cardiovascular function in conscious cynomolgus monkeys and did not produce significant changes in respiratory rate, tidal volume, or minute volume in conscious rats. Evaluation of ITI-333 effects on gastrointestinal (GI) function showed that ITI-333 alone had no effect on GI propulsion in rats and yet ITI-333 blocked morphine-induced slowing of GI motility in rats. These data suggest that ITI-333 effectively mitigates some of the adverse symptoms associated with opioid use. ITI-333 lacks opioid-like abuse liability as it was not self-administered by rodents or non-human primates. Importantly, ITI-333 attenuates physical signs of naloxone-induced precipitated withdrawal in opioid dependent animals, indicating ITI-333 may alleviate symptoms of opioid withdrawal in humans.

[REDACTED]

[REDACTED]

[REDACTED]

[REDACTED]

[REDACTED]

[REDACTED]

Details on the profile of ITI-333 are provided in the current ITI-333 Investigator's Brochure.

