6.3.2 Exclusion Criteria

Subjects who meet any of the following criteria will not be eligible to participate in the study:

1. Clinically significant abnormality within 2 years of Screening that in the Investigator's opinion may place the subject at risk or interfere with study outcome variables; this includes, but is not limited to, history of or current cardiac, hepatic, renal, neurologic, gastrointestinal, pulmonary, endocrinologic, hematologic, or immunologic disease or history of malignancy;
2. Any clinical condition or procedure (eg, gastric bypass or cholecystectomy) that may affect the absorption, distribution, biotransformation, or excretion of ITI-333. Subjects with a history of appendectomy are eligible for study participation;
3. Current or recent (within 3 months prior to Screening) unstable angina; a history of myocardial infarction within 3 months prior to Screening; or a history of a clinically significant cardiac arrhythmia;
4. History of psychiatric condition that in the Investigator's opinion may be detrimental to participation in the study;
5. Any history of Substance Use Disorder as defined by the *Diagnostic and Statistical Manual of Mental Disorders, Fifth Edition, Text Revision* ([American Psychiatric Association, 2022](#));
6. Any suicidal ideation including but not limited to wishes to be dead or any thought of killing self within 6 months of Screening, any suicide attempt within 2 years prior to Screening based on the Columbia-Suicide Severity Rating Scale (C-SSRS), and/or any current concerns for subject's safety as assessed by the Investigator;
7. Previously participated in an investigational study of ITI-333;
8. Likely allergy or sensitivity to ITI-333 or its excipients based on known allergies or hypersensitivities to drugs with shared pharmacology which may be suggestive of an increased potential for an adverse reaction to ITI-333;

- [REDACTED]
- [REDACTED]
11. Clinically significant abnormal findings in vital sign assessments, including oxygen saturation (SpO₂) < 96% and respiratory rate < 12 breaths per minute, supine systolic blood pressure > 140 mm Hg or < 90 mm Hg, or supine diastolic blood pressure > 90 mm Hg or < 50 mm Hg, or supine pulse rate > 100 bpm or < 45 bpm at Screening or Day -1. One repeat of vital signs assessment may be performed to confirm out of range values;

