7.5 Monitoring Treatment Compliance

All doses will be administered by qualified study center staff to ensure that the correct doses are given at the scheduled time. The treatments will be administered by qualified study personnel under the direction of the Investigator. A study personnel witness will verify that the study drug has been given correctly.

Details of the exact date and time of administration (day/month/year, h:min) [REDACTED] will be recorded in the eCRF.

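### The adverse-event review for abuse potential would be more informative with a prespecified list of acute subjective-effect terms, a count of subjects with any such term, and a listing that includes withdrawal

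*SAP*

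**What the plan says.** SAP 10.1 gives one adverse-event method for abuse potential: "AEs will be reviewed for any evidence suggestive of abuse potential using standardized MedDRA queries (SMQs) for drug abuse, dependence, and withdrawal". Protocol 9.4.5.1 has the matching sentence: "AEs will be reviewed for any signal suggestive of abuse potential using standardized MedDRA queries for drug abuse, dependence, and withdrawal".

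The SAP names two outputs. The first is a table at preferred-term level: "Adverse events identified through SMQs by cohort and treatment, ITI-333 combined across all cohorts, and placebo combined across all cohorts will be summarized by preferred" [...]. The second is a listing: "A supportive listing will be presented for drug abuse and dependence AEs". Withdrawal is one of the three search topics, but the listing sentence does not name it.

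The same SAP section tabulates all TEAEs by SOC and preferred term, by severity and by relationship, for each cohort and treatment and for pooled ITI-333 and pooled placebo. A subject with several events under one preferred term is counted once for that term.

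The setting matters for what the search can find:

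- Protocol 7.5: staff give every dose, and "A study personnel witness will verify that the study drug has been given correctly".
- Protocol 6.3.1 and the synopsis: subjects are confined for the inpatient period and discharged on Day 17.
- Protocol 6.3.2: criterion 5 excludes "Any history of Substance Use Disorder as defined by the" DSM-5-TR, and criterion 18 excludes a positive drug, alcohol or cotinine test.
- Protocol 4: ITI-333 is described as a biased mu-opioid "receptor ligand with partial agonist activity, acting as an antagonist to block effects of high doses of morphine".

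**The concern.** The stated aim is broad (anything suggestive of abuse potential), while the search is confined to three topics. Two of them, abuse and dependence, are behaviours or diagnoses that this design leaves little room for: subjects do not hold the drug, cannot raise the dose, and were selected for having no substance use disorder. What a 14-day inpatient study of a mu-opioid partial agonist could more readily show is acute subjective and central nervous effects after a dose, such as euphoric mood, feeling drunk or dissociation. The readable text does not bring such terms into the abuse-potential review.

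The stake is interpretation. Protocol 4 states, from animal self-administration data, that the drug lacks opioid-like abuse liability. A sparse abuse-potential table in humans could be taken as agreeing with that, while relevant events sit under several preferred terms in another table.

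**Working it through.** No figure in the plan concerns this review, so most of the check sets the texts side by side.

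1. **Size of the study.** SAP 14 and Protocol 9.2 plan 4 cohorts of 6 active and 2 placebo subjects. 4 × (6 + 2) = 32, as stated; active 4 × 6 = 24, placebo 4 × 2 = 8.

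2. **The three search topics against the design.**
   - *Abuse and dependence:* witnessed once-daily dosing, confinement, exclusion for substance use disorder and drug testing make such events unlikely.
   - *Withdrawal:* the last dose is on Day 14. Discharge on Day 17 is 17 − 14 = 3 days later, and the follow-up visit on Day 24 is 24 − 14 = 10 days later. The TEAE window also closes 10 days after the last dose. Withdrawal events after stopping can therefore be observed, and the search for them is relevant.

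3. **Where acute subjective effects would go.** Any reported TEAE enters the SOC and preferred-term table with its cohort and placebo columns, so these events are reported. They enter the abuse-potential table only if their preferred term belongs to one of the SMQs. Neither document lists the SMQ terms.

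4. **What separate rows cannot show.** Each subject counts once per preferred term. If k related terms have counts c₁, …, cₖ in a group of n, the number of subjects with any of them lies between max(cᵢ) and min(n, Σcᵢ). As a hypothetical example, take four terms each reported by 1 of 6 active subjects in a cohort. The lower limit is 1 of 6 (17%) and the upper limit is min(6, 4) = 4 of 6 (67%). Four rows of 1 fit both. Protocol 8.1.1.4 has subjects volunteer events in reply to a non-leading question, so one kind of experience may be described differently and coded to different terms.

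5. **Whether this design could show such events.** The documents give no rate, so a range is assumed. For a true reported rate p, the same in every active subject and independent between subjects, P(at least one case) = 1 − (1 − p)ⁿ.

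| Assumed rate p | One active cohort, n = 6 | All active, n = 24 |
|---|---|---|
| 1% | 6% | 21% |
| 2% | 11% | 38% |
| 5% | 26% | 71% |
| 10% | 47% | 92% |
| 20% | 74% | 99.5% |
| 30% | 88% | >99.9% |

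For example, at 10% in 24 subjects: 1 − 0.9²⁴ = 0.92. A common rate is a simplification, because a dose-related effect would concentrate in the higher cohorts. From about 5% upwards, at least one case among the 24 active subjects is more likely than not, so a prespecified list would probably have something to collect.

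**The case against.** The strongest reply is that nothing is lost. Every TEAE is tabulated by preferred term beside placebo, and in 32 subjects a cluster of euphoric mood in the top cohort would be easy to see. SAP 16.2 refers to adverse-event data listings, so a reader could count subjects by hand, and Protocol 9.6 gives the DMC unblinded safety data for each cohort. This stands: a reader might infer that the plan would fail to detect a euphoria-type signal, and the documents do not support that. It does not supply a grouped count or a list of terms chosen before treatment is known.

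Second, a reader might infer that the SMQ table is bound to be empty, or put an expected number of hits on it. That requires the SMQ contents, which the documents do not give; some mood or perceptual terms may already be included. The inference is also wrong for withdrawal, as shown above.

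Third, much text is blacked out. The readable SAP passes from Section 10.4 to Section 13 and the protocol from 8.2 to 8.6, some objectives and safety measures are hidden, and the table specifications are in a separate document. Another abuse-related assessment may exist, so it cannot be said that abuse potential goes unassessed. The sentences defining this adverse-event search are readable, however, and another assessment would not change the search as written.

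Fourth, no readable objective concerns abuse liability, and the claim in the Introduction is expressly nonclinical. That limits the weight of the point without removing it, since the plan itself sets out to look for evidence of abuse potential.

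**Conclusion.** The point holds as a cheap improvement to a descriptive safety summary. In the readable text the review uses only SMQs for abuse, dependence and withdrawal. Acute subjective effects are reported in the general TEAE tables, but they are not grouped, no count of subjects with any such effect is planned, and the supportive listing does not name withdrawal although the search covers it. Read alone, the abuse-potential table could understate the evidence.

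The size cannot be fixed from the documents, because it depends on which preferred terms the SMQs contain: the more acute-effect terms they already hold, the smaller the gap. The 1-to-4-of-6 range is an illustration of the counting problem, and the detection probabilities rest on assumed rates. No estimate, analysis population, sample size or error rate is affected.

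**What to change.** In SAP 10.1:

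- Keep the three SMQ searches and their table.
- Add a list of abuse-related preferred terms, fixed before database lock and unblinding by staff who have not seen treatment codes. Candidates are euphoric or elevated mood, feeling drunk, feeling abnormal, feeling of relaxation, dissociation or depersonalisation, hallucination or perceptual disturbance, mood swings, disturbance in attention, and somnolence or sedation. Check the list against the SMQ contents in the MedDRA version used, and record the overlap.
- Summarise the list by cohort and treatment, combined ITI-333 and combined placebo, with one row for subjects with any listed term.
- Extend the supportive listing to withdrawal events and the added terms, showing time from the most recent dose.
- Record the addition in SAP 17, which at present reports no changes to the protocol's analyses.

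The cost is SAP wording, one more table and a longer listing, all from adverse events already collected and coded. Non-specific terms such as somnolence will add some noise; the placebo column puts them in context.
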